- Maximum serum concentration (C_{max}) at each dose
- Trough serum concentration (C_{trough}) at each dose

Pharmacodynamic Assessments: Blood samples for pharmacodynamic (PD) analysis will be obtained at;
 
• Day 1 of Cycle 1 of the Induction Study Period and Day 1 of Cycles 1-2 of the Maintenance Study Period: predose and 1 hour after the end of infusion• Day 1 of Cycle 2-4 of the Induction Study Period and Day 1 of Cycle 3 of Maintenance Study Period: predose• First EOT and Second EOT visit: any time of the day 
Secondary PD Endpoint:
 
• B-cell kinetics

Safety Assessments:
 
• Adverse events, serious adverse events, concomitant medications, hypersensitivity (via vital signs monitoring including systolic and diastolic blood pressure, heart rate, respiratory rate, and body temperature), physical examination findings, vital sign measurements, clinical laboratory analyses, chest x-ray findings, electrocardiogram findings, infection, infusion-related reactions, immunogenicity testing, immunoglobulin testing, and tuberculosis assessment.

Biomarker Assessment (Optional): Only for patients who sign a separate informed consent form (ICF) for the biomarker assessment (genotypes). A blood sample for evaluation of FcγR genotype (FcγRIIa, IIIa, and/or any necessary genotypes) will be collected after randomisation and before study drug administration on Day 1 of Cycle 1 during the Induction Study Period only.
 
Secondary Biomarker Endpoint:
 
• FcγR genotype (FcγRIIa, IIIa, and/or any necessary genotypes)

Sample Size:
 
A sample size of 174 patients (87 patients in each treatment group of CT-P10 and Rituxan) leads to 91% statistical power for the demonstration of similarity of ORR at 7 months (Prior to Cycle 3 of the Maintenance Study Period) based on ORR of 88% and an equivalence margin of $\pm 17\%$ using a 2-sided 90% confidence intervals (CIs) approach corresponding to 5% significance level of an equivalence test. The intent-to-treat (ITT) population will be the primary analysis population for the efficacy analysis. A supportive analysis for the efficacy analysis will be conducted using the per-protocol (PP) population for response rate. In the PP population with a 13% drop-out rate, 86% statistical power is expected.

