3.2. Secondary Objectives

[figure not shown]
- To evaluate ORR (CR + CRu + PR) according to the Modified Response Criteria for Malignant Lymphoma during the study period
- To evaluate additional efficacy parameters (progression free survival [PFS], time to progression [TTP] and overall survival [OS] according to the Modified Response Criteria for Malignant Lymphoma)
- To evaluate pharmacokinetics (PK), pharmacodynamics (B-lymphocyte [B-cell] kinetics), overall safety including immunogenicity, and biomarkers of CT-P10 in comparison with Rituxan

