4. OVERALL STUDY DESIGN AND PLAN

This is a Phase 3, prospective, randomized, parallel-group, active-controlled, double-blind, multicenter, international study to evaluate the similarity of efficacy and safety of CT-P10 to Rituxan in patients with Grade 1 to 3a (Ann Arbor stage II-IV) low tumour burden follicular lymphoma (LTBFL) based on Groupe d'Etudes des Lymphomes Folliculaires (GELF) criteria. The study will include study centers in Europe, Africa, the Middle East, Asia Pacific, and Latin and North America.

The study will consist of 4 periods: Screening Period, Induction Study Period, Maintenance Study Period, and Follow-up Period. The overview of study design is shown in [Figure 1](#).

Figure 1: Schematic of Study Design

- Screening Period (up to 6 weeks)
- Induction Study Period (up to 4 weeks):
 - Study drug will be administered weekly for 4 weeks (at a dose of 375 mg/m² by an intravenous [IV] infusion).
 - The End of Treatment (EOT) 1 visit will occur 1 week (±1 day) after the last dose of study drug administration in the Induction Study Period.
 - Patients will be assessed 8 weeks (±7 days) after the last dose of study drug administration in the Induction Study Period, and the investigator will determine whether patients qualify to continue in the Maintenance Study Period.
 - Patients who experienced CR, CRu, PR, or stable disease (SD) in this assessment will qualify for the Maintenance Study Period and the assessment visit will be called the Maintenance 1 visit.
 - Patients who experienced progressive disease (PD) or unknown status of disease will not enter into the Maintenance Study Period. These patients will be withdrawn from the study treatment and will enter the Follow-up Period, provided patient consent has not been withdrawn. For these patients, the assessment visit will be called the EOT2 visit.

- If a patient withdraws before the completion of the Induction Study Period, this patient will not enter the Maintenance Study Period. However, the patient will enter the Follow-up Period, provided patient consent has not been withdrawn.
- Maintenance Study Period (up to maximum 12 cycles for 2 years):
 - The first dose in the Maintenance Study Period will be administered 8 weeks (± 7 days) after the last dose of study drug administration in the Induction Study Period.
 - Study drug will be administered every 8 weeks up to maximum 12 cycles for 2 years (at a dose of 375 mg/m^2 by an IV infusion).

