11.2. Pharmacokinetic Parameters

The secondary pharmacokinetic endpoints are Maximum serum concentration (C_{max}) and Trough serum concentration (C_{trough}) at each dose. C_{max} is the observed maximum serum concentration following drug administration, and C_{trough} is the observed trough serum concentration following drug administration; calculated from the predose concentration of the next dose. If the patient discontinued before next dose, concentration at EOT1 (for Cycles 1 to 3 in Induction Study Period) or EOT2 (for Cycle 4 in the Induction Study Period where there is no predose for Cycle 1 Maintenance) will be used. Serum concentrations BLQ at baseline (predose at Induction Study Cycle 1) will be set as zero. Serum concentrations BLQ after study drug exposure will be set as LLoQ. Missing values for any PK parameters will not be imputed.

The table will summarize the PK parameters using descriptive statistics by treatment group: n, mean, standard deviation, geometric mean, CV%, minimum, median and maximum. Geometric mean will not be reported if the dataset includes zero values, CV% will not be reported if the mean is zero.

Pharmacokinetic parameters for the PK population will be listed.

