23. Response evaluation will use the Modified Response Criteria for Malignant Lymphoma. All response results must be recorded in the electronic case report form. Response results by the investigator will be used to determine the eligibility and treatment practice. In addition, tumour assessment images will be evaluated centrally during Induction Study Period and Maintenance Study Period by an independent reviewer for reporting purposes. During the Follow-up period, tumour assessment images will be reviewed at the local level only. Response evaluation will be performed prior to Cycle 1 (Month 3; EOT2), Cycle 3 (Month 7), Cycle 6 (Month 13) and Cycle 9 (Month 19) and at the EOT3 visit in the Maintenance Study Period, and every 6 months during the Follow-up Period until treatment with new anticancer therapy or disease progression.
24. Pharmacokinetic (PK) samples will be collected at predose (before the study drug infusion within the day), and at 1 hour (± 15 minutes) after completing the study drug infusion for each Induction Study Period cycle. At the EOT 1 and EOT 2 visits, PK samples will be obtained anytime during the day. Blood samples for PK analysis will be obtained at predose, and 1 hour (± 15 minutes) after the end of study drug infusion (EOI) on Day 1 of Cycle 1 (Month 3) and Cycle 2 (Month 5) during the Maintenance Study Period. On Day 1 of Cycle 3 (Month 7), PK analysis will be obtained at predose. Testing will be performed at the central laboratory. Details of blood sampling schemes are provided in [APPENDIX 2](#).

25. Blood samples for assessment of B-cell kinetics will be collected at predose (before the study drug infusion within the day) study drug on Day 1 of each treatment cycle in the Induction Study Period; at predose, and 1 hour after the end of infusion during Cycle 1 in the Induction Study Period. At the EOT1 and EOT2 visits, Pharmacodynamics samples will be obtained anytime during the day. In addition, blood samples for Pharmacodynamics analysis will be obtained at predose, and 1 hour after the end of study drug infusion on Day 1 of Cycle 1 (Month 3) and Cycle 2 (Month 5), at predose on Day 1 of Cycle 3 (Month 7) during Maintenance Study Period. Testing will be performed at the central laboratory.

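### PK is to be evaluated against Rituxan, but the plan gives only by-arm summaries; a supportive geometric mean ratio with a 90% CI would quantify the comparison

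*SAP*

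**What the plan says.** The objective is comparative. SAP 3.2 reads "To evaluate pharmacokinetics (PK), pharmacodynamics (B-lymphocyte [B-cell] kinetics), overall safety including immunogenicity, and biomarkers of CT-P10 in comparison with Rituxan", and the protocol synopsis has the same objective.

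The endpoint sentence in SAP 11.2 is "The secondary pharmacokinetic endpoints are Maximum serum concentration (C_{max}) and Trough serum concentration (C_{trough}) at each dose"; the synopsis also lists "Trough serum concentration (C_{trough}) at each dose". SAP 11.2 defines the trough of a dose as "calculated from the predose concentration of the next dose". For a patient who discontinues before the next dose, it substitutes the EOT1 or EOT2 concentration for induction doses only.

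The planned analysis is by arm: "The table will summarize the PK parameters using descriptive statistics by treatment group". The statistics include the geometric mean and CV%. SAP 11.1 adds concentration summaries, profile plots and a listing, and the synopsis likewise has PK parameters summarised by treatment group. Neither text mentions a ratio, a difference, an interval or a model for PK.

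On sampling, SAP Appendix 1 (footnote 24) and Appendix 2 schedule predose and 1-hour post-infusion samples at Induction Cycles 1–4 and Maintenance Cycles 1–2. The last scheduled sample is at Maintenance Cycle 3: "On Day 1 of Cycle 3 (Month 7), PK analysis will be obtained at predose". EOT1 and EOT2 samples may be taken at any time of the day.

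**The concern.** A comparative objective normally leads to an estimate of the difference between arms and a measure of its uncertainty. For the primary endpoint, SAP 10.1.1 gives both: a difference in proportions with a 90% CI. For PK it gives neither. A reader of the report can divide one geometric mean by the other, but will not be told how precisely that ratio is known. The by-arm arithmetic CV% does not give the interval directly.

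What is at stake is how informative a secondary result is. SAP 5.3 has the randomisation code broken for the first CSR, so a ratio first chosen after that point would carry less weight than one written into the SAP beforehand. No decision rule in the trial depends on PK.

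**Working it through.** The documents give no PK precision, power or dose-coverage figure to reproduce, so the check is a count followed by a precision calculation.

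**1. Doses in the randomised comparison.** Induction: 4 ("Study drug will be administered weekly for 4 weeks", SAP 4). First maintenance year (MP1): 6 (SAP 4). Total 4 + 6 = 10. Up to 6 further doses follow in the second maintenance year (MP2), but SAP 4 offers only CT-P10 then, so those doses have no Rituxan comparator.

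**2. Doses with a derivable parameter.**

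| Parameter | Sample needed | Doses covered |
|---|---|---|
| Cmax | 1 hour post-infusion, same dose | Induction 1, 2, 3, 4; Maintenance 1, 2 |
| Ctrough | predose of the next dose (Induction 2, 3, 4; Maintenance 1, 2, 3) | Induction 1, 2, 3, 4; Maintenance 1, 2 |

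Each parameter covers 6 of 10 doses (60%). Maintenance 3–6 are not covered. The 7-month assessment precedes Maintenance Cycle 3, and 4 + 2 = 6 doses are given before it, so coverage up to that point is 6 of 6.

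**3. Between-arm PK estimates.** Planned in the visible text: 0. Available from scheduled samples: 6 doses × 2 parameters = 12.

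**4. Precision those estimates would have.** For a log-normal parameter with the same between-patient CV and n evaluable patients in each arm, the 90% CI is the ratio multiplied and divided by

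F = exp( t(0.95, 2n − 2) × √ln(1 + CV²) × √(2/n) ).

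The CVs are assumptions. n = 87 is the randomised number per arm (SAP 5.2) and therefore a ceiling. Applying the planned 13% drop-out gives 87 × 0.87 = 75.7, about 76.

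Worked case, n = 87 and CV 30%: t = 1.654, √ln(1.09) = 0.2936, √(2/87) = 0.1516; product 0.0736; F = 1.076.

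| Assumed CV | F, n = 87 | F, n = 76 |
|---|---|---|
| 30% | 1.08 | 1.08 |
| 40% | 1.10 | 1.11 |
| 60% | 1.15 | 1.16 |

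With an observed ratio of 1 and 87 per arm, CV 60% gives an interval of about 87% to 115%. Covariate adjustment is ignored here.

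**5. Who contributes.** SAP 4 admits only patients with CR, CRu, PR or SD to maintenance. The Maintenance 1–2 parameters therefore come from patients selected after randomisation. The same applies to the Induction 4 trough where it uses the Maintenance 1 predose sample; the EOT2 substitute limits this for patients who do not continue. SAP 11.2 gives no substitute for maintenance troughs.

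**6. Log scale.** SAP 11.2 sets post-exposure values below quantification to the LLoQ, so these parameters contain no zeros to prevent log transformation.

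**The case against.** The strongest reply is that the SAP does what the protocol synopsis prescribes. The primary objective is to demonstrate similarity, whereas the PK objective is only to evaluate, with no similarity criterion. By-arm summaries with geometric means and CV% are a legitimate descriptive answer. PFS, TTP, OS, B-cell kinetics and safety are handled the same way, so asking for more on PK is partly a preference. This largely stands. It sets the point's weight, but does not supply the missing precision.

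A reader might also infer more than the documents support:

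- **That the PK objective goes unanswered.** It is addressed descriptively; what is missing is a quantified ratio. The comparison with Rituxan belongs to the objective. The endpoint sentence itself does not contain it.
- **That only 6 of up to 16 doses are covered.** The count is correct, but the 16 include six second-year doses for which no comparison with Rituxan is possible. The relevant count is 6 of 10.
- **That PK after the switch is claimed.** SAP 5.4 defines second-maintenance-period subsets for the ITT, PP and Safety populations and none for PK. SAP 11 ties PK sampling to Appendix 1, where it ends at Maintenance Cycle 3. The each-dose wording is loose, but the schedule bounds it.

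The precision figures rest on assumed CVs, and 87 per arm will not be reached at every dose. Only the protocol synopsis is visible, and the table shells are a separate addendum, so a ratio could be planned in text that cannot be seen here.

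**Conclusion.** The point holds as a minor improvement. A comparative secondary objective is served by two uncompared columns, although the scheduled samples would support 12 between-arm ratios at six doses. Under assumed CVs of 30–60%, each 90% CI would be the ratio multiplied and divided by about 1.08–1.15 with 87 evaluable per arm, or about 1.08–1.16 with 76, and wider if fewer contribute. These figures assume log-normal data, equal CVs and equal evaluable numbers in the two arms.

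The sampling schedule needs no change for this purpose: it covers every dose before the 7-month assessment. The primary analysis is unaffected.

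**What to change.** In SAP 11.2, for each of Induction Cycles 1–4 and Maintenance Cycles 1–2, add the CT-P10/Rituxan geometric mean ratio with its 90% CI for Cmax and Ctrough. Estimate it from a model of the log-transformed parameter with treatment and the randomisation factors (region, Ann Arbor stage, age). Label the table supportive, with no acceptance limit. Show the number evaluable per arm at each dose. Add a note that the Maintenance 1–2 ratios, and the Induction 4 trough where it uses the Maintenance 1 predose sample, depend on who stayed on treatment after randomisation.

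Naming the six covered doses beside the endpoint, in the synopsis and SAP 11.2, is an optional clarification.

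Cost: one extra table from scheduled samples. Its 12 intervals are not adjusted for multiplicity. At 90% coverage, about 12 × 0.10 = 1.2 would be expected to miss the true ratio by chance, so no single interval should be read as a test.

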12. PHARMACODYNAMIC ANALYSES

All pharmacodynamic tables and listings will be generated based on the Pharmacodynamic population by treatment group unless otherwise specified. Blood samples for B-cell kinetics will be obtained according to [APPENDIX 1](#). The secondary pharmacodynamic endpoint is B-cell kinetics.

A summary table presenting actual values and changes from baseline along with descriptive statistics will be presented for B-cell values by treatment group and time-point for all scheduled visits, including the records at predose and 1 hour after the end of infusion. Descriptive statistics will consist of n, mean, standard deviation, geometric mean, CV%, minimum, 25th percentile, median, 75th percentile, maximum and IQR. Geometric mean will not be reported if the dataset includes zero values. Any values recorded below the lower limit or above the upper limit of quantification will be set to the respective limit for all summary tables.

13. SAFETY ANALYSES

All analysis of safety data will be conducted for the Safety population and displayed by treatment group in 1st CSR. For the final CSR, all analysis of safety data will be conducted for the Safety population and Safety population – 2nd Maintenance Period subset and displayed by treatment group. The safety endpoints will be assessed using the following: AEs, SAEs, concomitant medications, hypersensitivity (via vital signs and ECG), physical examination findings, vital signs measurements, clinical laboratory analyses, chest x-ray findings, ECG findings, infection, infusion-related reactions, immunogenicity testing, immunoglobulin testing, tuberculosis (TB) assessment, ECOG status and pregnancy.

The analyses of concomitant medication are described in [Section 9.1](#).

Unscheduled results will not be summarized, but will be listed only, with the exception of the Common Terminology Criteria for Adverse Events (CTCAE) analysis of laboratory data detailed in [Section 13.2](#).

13.1. Adverse Events

An adverse event (AE) is defined as any untoward medical occurrence in a patient enrolled (i.e., when the ‘Informed Consent’ page of eCRF is recorded) into the study regardless of its causal relationship to study drug.

A treatment-emergent AE (TEAE) is defined as any event not present before exposure to study treatment or any event already present that worsens in intensity or frequency after exposure to study treatment.

The MedDRA version 18.1 or later will be used to code all AEs. AEs will be graded for intensity according to CTCAE version 4.03.

All AEs occurring during the study will be listed by treatment group. Listings for AEs will include following information: Study period (Induction to MP1, MP2, and Follow-up); SOC, PT and verbatim term; start and stop date; duration (days from start date until stop date of an AE); frequency (intermittent, continuous); outcome (recovered/resolved, recovering/resolving, recovered/resolved with sequelae, not recovered/not resolved, fatal, unknown); any treatment required (no, yes with specified treatment); intensity (CTCAE grade 1 to 5); action taken by investigator (no action taken, dose decreased, dose interruption [or prolonged], permanently discontinued, dose delay); relationship to study drug (unrelated, possible, probable, definite); whether the event is serious (yes, no); and whether patient is terminated from the study due to AE

(yes, no).

In summaries, AEs will be considered to be related if the relationship is possible, probable or definite. If relationship or intensity is missing, it will be summarized separately under a missing category.

Combined PTs using [APPENDIX 5](#) will be summarized in AE tables. Listings will include PTs as coded without applying the PT combining rule.

Summaries related AEs will be presented in overall and by each study period (Induction to MP1, MP2 and Follow-up). Any AE having a start date on or after Induction Cycle 1 visit date and before Maintenance Cycle 7 visit date or Follow-up 1 visit date (in case a patient with discontinuation before Maintenance Cycle 7) will be included in the Induction to MP1 Period. Any AE having a start date on or after the Maintenance Cycle 7 visit date and before Follow-up 1 visit date will be included in the MP2 Period. Any serious adverse drug reaction (SADR) reported in the eCRF having a start date on or after the Follow-up 1 visit date and up to last Follow-up visit date will be included in the Follow-up Period.

The number and percentage of patients with at least one event including TEAE, TESAЕ, TEAE leading to permanent discontinuation of the study drug and TEAEs of special interest will be presented by relationship to study drug, intensity, SOC and PT for the Safety population and Safety population – 2nd Maintenance Period subset. At each level of summarization for the number of patients, a patient is counted only once if they reported one or more events and only the most severe event recorded will be counted. Percentages will be calculated out of the number of patients in each population. The total number of events and number of patients with at least one event will also be displayed.

All AE related tables will be also displayed without relationship to study drug.

If the stop date of an AE is partial or missing, the following rules will be applied. The imputed stop date will be only used to impute start date.

- If the day of an AE is missing (e.g. XXFEB2017), the last day of the month (e.g. 28FEB2017) will be assumed.
- If the day and month are missing (e.g. XXXXX2017), December 31st will be assumed.
- If the stop date of an AE is missing (e.g. XXXXXXXXXX), the date will be considered as ‘Missing’.

In case a patient is dead, the stop date will be imputed as the date of death if the imputed stop date

is after the date of death.

If the start date of an AE is partial or missing, the following rules will be applied.

- If the day of an AE is missing (e.g. XXFEB2017), the month and year of the partial date will be compared to the date of the first exposure to study drug.
 - If the month and the year are equal for both dates, the AE start date will be imputed as the earlier date of: (i) the date of the first exposure to study drug, or (ii) the recorded/imputed stop date of the AE. If the recorded/imputed stop date of the AE is missing, the start date will be imputed as the date of the first exposure to study drug.
 - If the month or year is not equal, the AE start date will be imputed as the first day of the month (e.g. 01FEB2017).
- If the day and month are missing (e.g. XXXXX2017), the year of the partial date will be compared to the date of the first exposure to study drug.
 - If the years are equal for both dates, the AE start date will be imputed as the earlier date of: (i) the date of the first exposure to study drug, or (ii) the recorded/imputed stop date of the AE. If the recorded/imputed stop date of the AE is missing, the start date will be imputed as the date of the first exposure to study drug.
 - If the years are not equal, the start date will be imputed as the 1st day of January of the year (e.g. 01JAN2017).
- If the start date of an AE is missing (e.g. XXXXXXXXXX), the start date will be imputed as the earlier date of: (i) the date of the first exposure to study drug, or (ii) the recorded/imputed stop date of the AE. If the recorded/imputed stop date of the AE is missing, the start date will be imputed as the date of the first exposure to study drug.

The recorded/imputed dates of AEs will be used for decision whether the event is TEAE and classification of study periods.

